4.0 OVERVIEW OF STUDY DESIGN AND INTERVENTION

4.1 Design

PROTOCOL SUMMARY

TIMEPOINT	COHORT 1	COHORT 2
Pretreatment	All Patients	All Patients

	
1) Patient simulation. 2) FDG scan with immobilization. 3) Recommended pretreatment MR scan with immobilization when possible (unless contraindicated, for main campus only). 4) ¹⁸F-FMISO scan (only 1 injection). Patient injected on the PET scanner: (a) Dynamic scan from 0-45 min (b) 10 min scan at about 90 min (c) 10 min scan at about 150-180 min 5) ¹⁸F-FMISO image-guided core biopsy (optional, if consented)
	
1) ¹⁸F-FMISO scan (only 1 injection). Patient injected on the PET scanner: (a) Dynamic scan from 0-45 min (b) 10 min scan at about 90 min (c) 10 min scan at about 150-180 min

During Treatment	
Select Patients
 
1) Repeat ¹⁸F-FMISO scan (only 1 injection) that occurs 5-10 treatment days after RT start*. Patient injected on the PET scanner: (a) Dynamic scan from 0-45 min (b) 10 min scan at about 90 min (c) 10 min scan at about 150-180 min 2) ¹⁸F-FMISO image-guided core biopsy (optional, if consented) 3) Recommended approximately weekly MRI when possible (unless contraindicated, for main campus only). Recommended DCE-MRI between treatment weeks one and two and between treatment weeks three and four, when possible.
	
Patients who Receive Radiation
 
1) Repeat ¹⁸F-FMISO scan (only 1 injection) that occurs 5-10 treatment days after RT start*. Patient injected on the PET scanner: (a) Dynamic scan from 0-45 min (b) 10 min scan at about 90 min (c) 10 min scan at about 150-180 min

Post-treatment	
All Patients
 
1) Recommended MR Scans at 3, 6, and 12 months (+/- 4 weeks) post end of RT (unless contraindicated, for main campus only) 2) Longitudinal chart review for two years post RT for adverse event assessment and disease status
	
Patients Who Receive 30Gy
 
1) Neck dissection three to four months post-chemoradiation (+/- 4 weeks). (a) If no residual disease, standard of care (b) If residual disease, booster dose of chemoradiation 2) Standard of care

Please note that a window period of 5-10 treatment days was chosen to accommodate holidays, weekends, and patient scheduling issues. Also, note that the repeat dynamic ¹⁸F-FMISO scan is performed early during the course of chemoradiotherapy (5-10 treatment days). For Cohort 1, this scan will be used to see whether there is a reduction of the ¹⁸F-FMISO avid or GTV_h within the gross tumor volume. For patients in Cohort 2 receiving a repeat scan, this repeat scan will be used to detect tumor hypoxia.

Safety measurements of typical vital signs, such as oral body temperature, respiratory rate, heart rate, and blood pressure will be performed before the administration of ¹⁸F-MISO, and at the end of each ¹⁸F-MISO PET/CT scan session. The patient will also be assessed for adverse events at the end of the ¹⁸F-MISO PET/CT sessions. Additionally, one business day (excluding holidays and weekends) following the completion of the ¹⁸F-MISO PET/CT scans, patients will receive a follow up phone call to assess adverse events.

Rationale for Change in ^{18}F -FMISO PET/CT Imaging Protocol

The preliminary ^{18}F -FMISO PET image data acquired in patients with head and neck cancers have shown variable hypoxia tracer uptake at the fixed 2.5 hour time point used in the initial study. In order to convert the ^{18}F -FMISO images to parametric images of tumor hypoxia, a group in Tübingen, Germany has recently shown the importance of obtaining kinetic information of the tracer in the tumor (14-17) for an unambiguous interpretation of the hypoxia images.

PET/CT Scan Protocol

Dynamic scans will be acquired on one of the PET/CT scanners qualified by the Department of Radiology and the Molecular and Imaging Therapy Service at the main hospital of MSKCC. 3-D mode and with listmode option will be turned ON. The listmode option allows the patient data to be reconstructed in a cine mode (in variable time frames) so that pharmacokinetics of tumor uptake of the radiotracer can be studied. The patient will be set up in the radiotherapy treatment position with an intra-venous line for radiotracer injection. A PET/CT scan will be performed with the tumor at the field center. These images will be used for both attenuation correction and registration of the serial image set.

Approximately 5-10 mCi dose of ^{18}F -FMISO will be injected as a bolus, and the dynamic scan initiated coincident with the injection. Data will be acquired in dynamic mode for up to a maximum of 45 minutes from the time of injection, but may be shorter (e.g. if the patient is in discomfort in the immobilization device for this duration). The patient will then be removed from the scanner, and instructed to return at approximately 90-minutes for a second PET scan and again at approximately 180-minutes for a third PET scan. No further activity will be injected in the patient at these times. The 2nd and 3rd PET scans will consist of a 10-minute image of the tumor. A low dose CT scan will be performed at each of these two image sessions for attenuation correction and image registration.

In up to 10 selected patients, the first segment of the scan shall be performed over the heart with the later segments still being performed over the tumor. These scans will be used to calibrate the input function currently derived from the carotid artery.

MR Scan Protocol

Multiparametric MR scans for Cohort 1 and Cohort 2 main campus patients will be performed on the Philips 3T scanner located in the Department of Radiation Oncology according to the standard IVIM departmental protocol and utilization of the patient's immobilization device when the immobilization device is available and the patient agrees to utilize it. DWI-MR images will also be acquired according to the standard IVIM departmental protocol.

At the pretreatment MR scan for Cohort 1 and Cohort 2 main campus patients, an additional scan will be acquired based on a research sequence provided by Philips (the

manufacturer of the machine on which these MRIs occur) that will allow visualization of cortical bones in the head and neck region and potentially differentiate bone from air sinus cavity. This scan will be used to evaluate the potential of using MR alone images to differentiate and segment normal tissues used in radiotherapy treatment planning. This additional sequence will add an extra 5 minutes to the total scan time. This sequence is written, maintained, and updated by Philips. When an update to this sequence occurs, the sequence may become unavailable for a few weeks, at which time the updated version is installed and tested internally by MSK staff. Therefore, this sequence will only be run when it is available. The total pre-treatment MR scan duration will be approximately 30-60 minutes.

For Cohort 1 main campus patients, the follow-up MR scans, which will occur during concurrent chemoradiation, will last approximately 20-40 minutes. Information collected from all MR scans will not affect the standard of care, as baseline and post-treatment scans are currently a component of the standard of care. Additional scans will be acquired on our Philips 3T research scanner. Images will be sent to the research Pinnacle workstation for storage and evaluation. These images may be used for contouring of normal structures during the treatment planning process. DW-MRI images will be processed on the Philips research platform and corresponding diffusion and perfusion maps will be analyzed for therapy response assessment and treatment planning. Spatial changes during treatment will also be evaluated using functional diffusion maps or parametric response maps. No clinical decision will be made at this point based on MR findings.

PET/CT Image-guided Core Biopsy (Optional – Cohort 1 Patients Only)

The PET/CT scan will be performed in the Center for Image-Guided Intervention and Surgery at MSKCC, which houses a PET/CT scanner in an interventional radiology and operating room environment. The PET image-guided core biopsy procedure will be conducted as follows:

On the day of ^{18}F -FMISO PET/CT imaging, patients will be injected with the study tracer, ^{18}F -FMISO. After the final ^{18}F -FMISO PET image acquisition at each visit session (where applicable), biopsy samples will be removed from tumor tissue exhibiting high and low ^{18}F -FMISO uptake (if both are available). These high and low ^{18}F -FMISO uptake regions correspond to putative hypoxic and normoxic regions, respectively. Parametric image maps will also be retrospectively generated from compartmental models that define the rate of ^{18}F -FMISO radiotracer entrapment. These values will be used, in addition to the percent injected dose per gram, for correlation with IHC of hypoxia specific markers.

The aforementioned biopsy samples will be obtained by an interventional radiologist according to the features of the ^{18}F -FMISO PET/CT images. 1% lidocaine will be used for local anesthesia supplemented with midazolam and fentanyl citrate for light conscious sedation. The biopsy needle will be placed in position to remove core biopsy material of the node(s), and the patient will have an additional low dose CT to visualize the biopsy

needle trajectory and location. In this way, we will obtain information of the exact location of the biopsy specimen in regard to the CT and therefore co-registered PET image. If movement should occur between biopsy localizer CT and the CT attenuation scan, then these two CT images will be co-registered using mutual information density software. Immediately following biopsy, the specimen will be properly oriented and pinned. Based upon published experience, discussion with other investigators, and our own experience of obtaining tissue prior and during treatment, we anticipate it will take approximately fifteen minutes to perform each biopsy. The specimen acquired from these tumor samples will be taken for paraffin embedding, fresh frozen (if patient consents to any of optional banking studies), and histological processing to our Pathology Department. Ten 5 μ m thick sections from paraffin tumor blocks or core samples will be deparaffinized and rehydrated, and stored at -80 °C until processing. IHC analyses will also be performed for the following hypoxia relevant biomarkers, among others: HIF-1 α , LOX, and Ki-67.

Pretreatment Surgical Resection (Cohort 2 Patients Only)

The eligible patient will undergo a pre-surgery FDG PET scan and an ¹⁸F-FMISO PET/CT scan. Following these pre-surgical scans, the patient will undergo his/her standard of care surgery. The surgeon will annotate the location of each sample resected from the lesion by a text description for documentation of relative position. The specimen will be embedded in paraffin in an orientation that will allow sectioning parallel to the imaging plane of the PET/CT image. Tissue sections will be stained with H&E, hypoxia specific, and proliferation markers using the same procedures as the described for the biopsy specimens in this protocol.

Biospecimen Samples

Biospecimen samples from Cohort 1 (obtained via biopsy) and Cohort 2 (obtained via surgical resection) will not be used for diagnostic purpose. They will instead be utilized for a research purpose. They will be labeled with de-identified subject IDs, initials, date and time of specimen collection, and visit time point, which are linked to the identifiable PHI and will be kept confidential. The participant's personal identity will not be used in reports that are written about the research. The MSKCC IRB/PB will review all requests for research performed involving tissues ascertained through this protocol. With the permission of IRB/PB, research studies on cellular, genetic, immunologic, or other features of tumor or normal samples may be performed with no names attached to the samples but linked by codes to personal identifiers. The results of any research using tissues will not be placed in the medical record.

HIF-1 α

IHC staining will be performed on biospecimen samples using the antibody against HIF-1 α (Novus Biologicals, Littleton, Colorado, dilution 1:1600) utilizing previously reported techniques. Briefly, 4 micron formalin-fixed paraffin embedded tissue sections will be mounted on Superfrost Plus slides, deparaffinized with xylene and rehydrated. Tissue

will be then avidin/biotin blocked with blocking kit (Vector SP-2001). For HIF-1 α , DakoCytomation catalyzed signal amplification system (Dako, K1500) will be used according to the manufacturer directions. Slides will be counterstained with hematoxylin, dehydrated and cover-slipped. Only the nuclear staining for HIF-1 α will be considered a positive result. Expression of HIF-1 α will be determined by semi-quantitatively assessing the percentage of marked tumor cells and the staining intensity to calculate an immunoreactive score (IRS). Therefore, the percentage of positive cells will be rated as 1–10% positive cells (1 \times), 11–50% positive (2 \times), 51–80% positive (3 \times), and > 80% positive cells (4 \times). The staining intensity will be scored as weak (1 \times), moderate (2 \times), and intensive (3 \times). Scores for expression and scores for percentage of positive cells will be multiplied to calculate an IRS ranging from 0 to 12.

Lysyl Oxidase

5 μ m formalin-fixed paraffin-embedded tissues will be deparaffinized in xylene, then rehydrated before antigen retrieval by microwaving in sodium citrate buffer (pH 6.0). The slides will then be incubated with a peroxidase block, followed by the primary antibody lysyl oxidase (LOX) according to the company's protocol. After hematoxylin counterstain, the slides will be cover slipped. Cytoplasmic staining will be considered as positive. The intensity and proportion of immunostaining will be scored on a semiquantitative six-point scale. Negative samples will receive a score of 0, whereas weak, moderate, and intense staining samples will receive a score of 1, 2, or 3, respectively. For the percentage tumor cell positivity the following scoring will be used: negative=0, 1–25%=1, 25–50%=2, >50%=3. Both the staining intensity and percentage positivity scores will be summed and tumors with scores ranging from 0 to 5 will be assigned to group 0=low lysyl oxidase, whereas those with a score of 6 will be assigned to group 1=high lysyl oxidase.

Ki-67

5 μ m formalin-fixed paraffin-embedded tissue will be subjected to IHC for Ki-67 staining using the MIB1 mouse mAb (Immunotech, Westbrook, ME) at a 1:500 dilution. Standard avidin-biotin-peroxidase complex techniques will be used. Antigen retrieval in heated citrate buffer at pH 6.0 will be applied. Slides will be counterstained with hematoxylin. Only nuclear staining of tumor cells will be considered positive. Ki67 expression will be determined by semi-quantitatively assessing the percentage of positive tumor cells.

Tissue Banking

With the patient's consent, we will bank the additional and left over tissue after the biopsy (Cohort 1) or surgical resection (Cohort 2) in Tissue Procurement Service (TPS). To further access this tissue, we will submit a plan to the Human Biospecimen Utilization Committee (HBUC). For retrospective feasibility studies, tissue use at MSKCC is governed by the HBUC. The HBUC has trans-departmental and multidisciplinary representation. As institutional policy, the HBUC will give special consideration to tissues requested for correlative analysis as part of a clinical trial, or to develop a tissue

bank at an academic institution, cooperative group or corporate entity. While the specimens for this protocol will reside in local repositories, we will nevertheless seek HBUC approval for use of the resources in this study as other investigators in the Center. We recognize that specimen resources are ultimately institutional resources, wherever they are stored and by whatever means they are ascertained. Approval by the HBUC committee will follow institutional standards. Each specific research use proposed for use of these banked specimens will be reviewed in the context of the scientific study design and human subjects' protection implications.

In a series of check boxes at the end of the consent form, patients in both Cohort 1 and Cohort 2 are asked if: 1) they permit their biospecimen to be stored and used in future research to learn about or prevent cancer or side effects of treatment, or to develop new treatments; 2) if they permit their samples to be stored and used in future research to learn about, prevent, or treat diseases other than cancer; or 3) if they permit their samples, with personal identifiers protected, to be used for research about inherited genetic factors; 4) if they permit their samples to be used for genetic analysis of the tumor and normal samples to learn about the causes of cancer; 5) if they agree to be contacted in the future as part of research studies for additional health information or to be asked to participate in future biospecimen research studies; 6) if they consent to be contacted to discuss research findings that may come from their sample; and 7) if he/she (the patient) is not available (e.g. deceased), if they wish to have their designee designated on the consent form to be contacted.

Participants will not be provided with specific results of research tests performed on their collected human biologic specimens. With their permission, the patient may be contacted in the future to ask if they are interested in joining new biospecimen research studies, if they would consent to research that would allow updates of their health status and if they consented to be contacted to discuss research findings which may come from their sample.

It will be stated that researchers at MSKCC may either keep indefinitely or dispose of any tissues, including DNA that the samples contain. Tissues will be stored with identifiers in secure tissue banks. It is stated that the samples could be lost or ruined because of mechanical failure, and that MSKCC cannot guarantee that samples will be stored indefinitely. The samples will be store for as long as deemed useful for research purposes.

The protocol consent form asks participants for permission for re-contact to discuss research findings if their samples are used in an HBUC project and an incidental research finding is made that may be critical to their preventive care. If a participant agrees to be re-contacted, he/she will not be told the specific results of the research test, but will be informed that his/her samples were used in a project and a potential risk was uncovered. If the participant is interested in further discussion of the research findings, he/she will be asked to come into MSKCC Clinical Genetics Service for counseling and specific genetic testing.

In the event an investigator's research identifies a finding that he or she believes should be communicated to the subject, the investigator shall communicate this to the Clinical Research Administration-IRB. The finding will be reviewed by a group convened by the IRB to determine whether the incidental finding should be discussed with the subject. In the event that group convened by the IRB determines that the finding should be discussed with the subject, and the subject has consented to be re-contacted, then the treating/consenting physician shall be contacted by the Clinical Research Administration-IRB representative and asked to refer the subject to the Clinical Genetics Service for further discussion of the research finding. After appropriate counseling and consent, the Clinical Genetics Service will request permission to confirm the result in a New York DOH-approved laboratory prior to communication of the specific test result. If the patient is not available (e.g. deceased), then the surrogate designated on the consent will be contacted and the above will occur.

The following information will be provided to the Clinical Research Administration-IRB representative and Clinical Genetics:

- Participant Name/MRN #
- Type of Biospecimen
- Incidental finding
- Project# (HBUC/Waiver #) that this analysis occurred under
- Collection Protocol #

Clinical Genetics Service Contact: [contact]

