2.0 OBJECTIVES

Primary

- To improve the accuracy of hypoxia imaging for head and neck cancers through pixel by pixel kinetic analysis of ^{18}F -FMISO tracer of dynamic PET images (Cohort 1 and Cohort 2).
- To detect on repeat ^{18}F -FMISO PET/CT scans whether there is a reduction of the ^{18}F -FMISO-avid or GIV_h 5 to 10 days into treatment with standard chemoradiotherapy for a series of locally advanced head and neck cancers (Cohort 1).
- To show that it is feasible to deliver 70Gy to primary site and 60Gy to the neck nodes in HPV+ patients who exhibit no evidence of hypoxia on their baseline ^{18}F -FMISO PET/CT scans or those who have early resolution of hypoxia on their early repeat ^{18}F -FMISO PET/CT scans (Cohort 1).
- To show that it is feasible to deliver 30Gy to the surgical bed and neck nodes in low-risk HPV+ patients who exhibit no evidence of hypoxia on their repeat ^{18}F -FMISO PET/CT (Cohort 2).
- To correlate the intensity of the ^{18}F -FMISO PET signal with the degree of immunohistochemical staining of hypoxia biomarkers for tissue obtained via biopsy (Cohort 1) and surgical resection (Cohort 2): HIF-1 α , Lysyl Oxidase, and Ki67 (an independent marker of tumor aggressiveness), among others.

Secondary

- To compare tumor heterogeneity derived from pixel-by-pixel kinetic analysis of PET scan and DWI-MRI (Cohort 1).
- To assess changes in tumor heterogeneity over the course of external beam RT using serial multiparametric MR and DCE-MRI scans (Cohort 1).
- To determine the potential of DCE-MRI data as a priori or early markers of tumor response to chemoradiation as well as long term disease-free survival after treatment (Cohort 1).
- To assess normal tissue response as a function of dose for parotid, submandibular glands, muscles and bones in the head and neck region during and after EBRT using serial multiparametric MR scans (Cohort 1).
- To bank specimens for further IRB/PB approved exploration of genetic analysis (Cohort 1 and Cohort 2).

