Please note that initially this pilot trial was written for 35 patients and after a meeting requested by the IRB with the PI and the coPI's, and with the advice from the IRB, it was decided to close the trial at patient 19 and write a new trial for cohort B. This new trial is MSKCC IRB 17-409.

Immunohistochemistry

Several studies examined the relationship between p16 expression by IHC and HPV DNA viral load by real-time PCR and found great correlation. These studies all uniformly showed that either is a good prognostic marker for treatment outcome. RTOG 0129 was a large randomized controlled clinical trial that was recently published for head and neck cancer of which there was a large tissue sample size that examined the relative strength of HPV DNA using in situ hybridization vis-a-vis p16 IHC as a prognostic marker (13). The study also showed that there was a very strong agreement between the presence of HPV DNA and p16 expression in head and neck tumors. Results of analyses using p16 expression as a stratification factor were consistent with those based on HPV status. Given p16 expression measured by IHC is a relatively simple procedure, we will stratify patients based on p16 status. This is also convenient for the patients as we will not have the need to subject the patients to further biopsy for HPV DNA analysis.

One important characteristic of tumor development is angiogenesis. Induced by hypoxia, the tumor cells secrete a variety of cytokines and growth factors that induce proliferation (evidenced by overexpression of Ki-67), migration, and blood vessel formation (23-25). Ki-67 is one known prognostic marker in head and neck squamous cell carcinoma (HNSCC) and is inversely related to the presence of hypoxia. The rationale is that a stronger and more widespread Ki-67 staining intensity signifies a higher fraction of proliferating cells in the tumor. Since cellular proliferation either does not occur or is greatly reduced within hypoxic tissue, we expect that high Ki-67 staining should be accompanied by low or absent ¹⁸F-FMISO image intensity and vice versa.

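### Nothing in the plan masks the person grading HIF-1 alpha, LOX and Ki-67 to FMISO uptake region, scan result or visit, although correlating staining with FMISO is a primary objective

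*Combined protocol and SAP*

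**What the plan says.** - **Role of the comparison.** Section 2.0 lists the correlation of FMISO intensity with IHC staining among the primary objectives, using biopsies in Cohort 1 and resections in Cohort 2.
- **Scoring (section 4.1).** HIF-1 alpha is scored by "semi-quantitatively assessing the percentage of marked tumor cells and the staining intensity": a percentage class (1 to 4) is multiplied by an intensity grade (1 to 3). For LOX, "The intensity and proportion of immunostaining will be scored on a semiquantitative six-point scale"; only a total of 6 counts as high. Ki-67 is a semi-quantitative percentage of positive tumor cells. No automated reading, second reader or agreement check is described.
- **Expected direction.** Section 3.0 (Immunohistochemistry) says of Ki-67 that "we expect that high Ki-67 staining should be accompanied by low or absent" FMISO intensity, and the reverse.
- **Label.** Section 4.1 (Biospecimen Samples) has specimens "labeled with de-identified subject IDs, initials, date and time of specimen collection, and visit time point".
- **Sampling and orientation.** Cohort 1 cores come from high- and low-uptake tissue, if both are available, after the last image of each session. They are oriented and pinned. Only Cohort 2 resections are embedded in "an orientation that will allow sectioning parallel to the imaging plane" of the PET/CT.
- **Repeat scans.** Under section 9.0, a Cohort 1 patient has a repeat FMISO scan only if the baseline scan was positive for hypoxia.
- **Test.** Section 14.0 plans a Wilcoxon rank sum test for each marker, with an adjustment such as Bonferroni.

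**The concern.** Grading intensity as weak, moderate or strong, and placing a percentage in a broad class, requires judgement on borderline slides. A reader who knows the uptake region, the scan result or the visit can resolve those slides in the expected direction without intending to. The resulting error is correlated with the FMISO variable, so it looks like the association the objective seeks.

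A multiplicity adjustment lowers the threshold but leaves the shift in place, and a larger sample makes a fixed shift easier to detect. Section 3.0 describes this as the first human study to correlate FMISO PET with tissue markers of hypoxia, so a positive result would be read as validation of the tracer.

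**Working it through.** **1. What the reader could learn from the specimen procedure**

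| Item | Reveals uptake class? | Reveals anything else relevant? |
|---|---|---|
| Label: ID, initials, date and time, visit | No; class is not listed, and nothing ties collection time to region | Yes, in Cohort 1: a repeat-visit core comes from a patient whose baseline scan was positive and who is already on treatment |
| Sectioning in the PET plane | No; a cutting plane does not say where uptake was high | Stated for Cohort 2 only |
| Scan images, uptake values, choice of region | Yes, if the reader has them | No section withholds them |

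High and low cores from one session share a visit label, so the label alone does not separate them. The last row is the substantive gap.

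**2. How much one borderline call moves a score**

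- HIF-1 alpha: score = percentage class × intensity. Attainable values are 0, 1, 2, 3, 4, 6, 8, 9 and 12, consistent with the stated range of 0 to 12. One intensity grade moves the score by the percentage class, so by up to 4 points (4 × 2 = 8 becomes 4 × 3 = 12).
- LOX: score = intensity + percentage class. Attainable values are 0, 2, 3, 4, 5 and 6, which is six points as stated. One grade turns 5 (3 + 2 or 2 + 3) into 6 and moves the tumor from low to high.

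**3. Illustrative effect on the planned test**

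The documents give no sample size, alpha or power for this comparison, so there is no figure to reproduce. Everything here is assumed: n = 20 high/low pairs, within-pair correlation 0.5, normal scores, no true difference, and a pure reader shift of d SD between high and low. The test is the two-sided rank sum.

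Hand approximation: the test statistic has mean 0.977 × d / √(2/20), where 0.977 = √(3/π) is the rank-test efficiency factor. The test ignores the pairing, so its SD is √(1 − 0.483) = 0.719, where 0.483 = (6/π) × arcsin(0.5/2) is the rank correlation. The critical values are 1.96 at 0.05 and 2.394 at 0.05/3.

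For d = 0.5 the mean is 0.977 × 0.5 / 0.316 = 1.545. The chance of exceeding 1.96 is P(Z > (1.96 − 1.545)/0.719) = P(Z > 0.58), about 28%. Simulation gives:

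| Drift d (SD) | Positive at 0.05 | Positive at 0.05/3 |
|---|---|---|
| 0 | about 1% | about 0.1% |
| 0.2 | about 3% | about 0.6% |
| 0.3 | about 8% | about 2% |
| 0.5 | about 27% | about 10% |

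Repeat runs put the d = 0.2 entry at 0.05/3 between 0.6% and 0.9%. The no-drift rates are below nominal because the rank-sum test ignores the pairing, so each row should be compared with the first row rather than with 5%. With 10 pairs at 0.05/3, the three drifts give below 1%, below 1% and about 3%. The divisor 3 is the number of named markers; the plan leaves the list open.

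**4. Same question on the HIF-1 alpha scale**

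Assume independent groups, uniform grades and no true association. A share of high-uptake slides is read one intensity grade up and the same share of low-uptake slides one grade down. With 20 per group and shares of 0, 10%, 25% and 50%, the rank-sum test is positive about 5%, 6%, 13% and 37% of the time at 0.05. At 0.05/3 with a 25% share the rate is about 5%, against a target of 1.7%.

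**The case against.** The strongest reply is that silence about masking does not show that readers were unmasked, and that the specimen details prove less than they seem to. Most of that stands. Four stronger readings are tempting, and the documents support none of them:

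- *That the label tells the reader which core is high-uptake.* It does not list uptake class, and cores from one session share the visit entry.
- *That all sections are matched to the PET image.* Sectioning in the imaging plane is stated only for Cohort 2 resections, whereas the high/low pairs are Cohort 1 biopsies.
- *That the direction is stated in advance for every marker.* It is explicit for Ki-67. For HIF-1 alpha and LOX it is only implied by calling them hypoxia markers.
- *That a false correlation is likely.* An unadjusted signed-rank test would be positive about 13%, 24% or 55% of the time under the same assumed drifts, but that test is not planned. The planned rank-sum test with adjustment gives far lower rates.

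Twenty pairs may also be generous. Biopsy is optional, and section 3.0 reports nearly 20 specimens, about half without tumor cells. Reading by eye is itself an inference from the semi-quantitative grades. The consequence is confined to the correlation, because section 4.1 keeps these research results out of the medical record.

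The reply does not remove the gap. A subjective primary measure has no masking requirement, and calling the subject IDs de-identified protects privacy rather than masking the reader.

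**Conclusion.** The point holds as a missing safeguard. Following the plan as written leaves the grading of three subjective markers, used for a primary objective, open to reader expectation. The visit entry on the label adds some information in Cohort 1.

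The documents show that drift is possible, not that it occurred, and they give no basis for its size. Under the assumptions stated (20 pairs, correlation 0.5, drift of 0.2 to 0.5 SD), false positives with the planned test run from about 3% to 27% at 0.05, against about 1% without drift. With a three-marker Bonferroni adjustment they run from about 0.6% to 10%, against about 0.1%. The adjusted rates are small for small drift, but they are a multiple of the no-drift rate throughout.

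No statistical adjustment recovers the unbiased scores. A masked re-read of retained slides could. This should be changed, but it does not affect patient treatment or the other primary objectives.

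**What to change.** Add to section 4.1 that each slide sent for scoring carries a random code hiding patient, visit, uptake region and scan result. Slides are to be read in random order, and scores locked before they are linked to FMISO data. Keep the existing label in the specimen log only.

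If scoring is already done, report whether readers were masked; where they were not, a masked re-read of retained slides would show whether the scores hold.

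The cost is relabelling by existing laboratory staff and a coding list to maintain. No extra reader or tissue is needed.
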